1.3 Study Schema

2. INTRODUCTION

2.1 Background

2.1.1 ACTT-4 – Baricitinib/Remdesivir vs. Dexamethasone/Remdesivir Trial

ACTT is a multi-site, global clinical trial platform designed to evaluate the clinical efficacy and safety of putative investigational therapeutic agents among hospitalized adults with laboratory-confirmed Covid-19. There have been three, phase 3, randomized, double-blind, placebo-controlled trials conducted using the ACTT platform, ACTT-1, ACTT-2 and ACTT-3. Each new ACTT study is considered another stage of the trial.

Data from ACTT-1 showed that hospitalized adults with COVID-19 who were randomized to receive remdesivir had a shorter time to clinical recovery than those who received placebo (10 vs. 15 days, recovery rate ratio 1.29 (95% CI 1.12 to 1.49, $p < 0.001$) (14). The odds of improvement on an ordinal scale by Day 15 were higher in the group that received remdesivir than in the placebo group (odds ratio 1.5; 95% CI 1.2 to 1.9, $p < 0.001$). After the release of these preliminary findings, the U.S. Food and Drug Administration (FDA) issued an Emergency Use Authorization (EUA) for remdesivir. On October 22, 2020, the FDA approved remdesivir (trade name, Veklury®) for use in adults and children 12 years of age and older for the treatment of COVID-19 requiring hospitalization. Veklury is the first treatment for COVID-19 to receive FDA approval. Remdesivir has also received, full or conditional approval in approximately 50 other countries.

While remdesivir is considered the standard antiviral for COVID-19, significant morbidity and mortality still occur despite its use. Early in the outbreak, it was observed that COVID-19 patients who developed severe respiratory disease including acute respiratory distress syndrome (ARDS) had increased levels of cytokines consistent with that seen in patients infected with other pathogenic coronaviruses (e.g., SARS) (37-39). It is postulated that this dysregulated inflammatory immune response contributes to the excessive mortality and targeting this response would further improve outcomes. While multiple strategies have been proposed to counter the hyper-inflammation, to date only two anti-inflammatory strategies have demonstrated efficacy in large randomized trials – dexamethasone and baricitinib.

In ACTT-2, subjects receiving the combination treatment of baricitinib and remdesivir had a shorter median time-to-recovery of 7 days (95% confidence interval (CI), 6 to 8 days) when compared with patients who received remdesivir and placebo (8 days; 95% CI, 7 to 9 days) with control [rate ratio for recovery [RRR] 1.16, 95% CI 1.01 to 1.32; $P=0.03$]. Patients who received combination treatment were 30% more likely to have clinical improvement by day 15 than those in the control arm (odds ratio [OR] 1.3; 95%CI 1.0 to 1.6). The patients who benefited the most from combination treatment were those requiring high-flow oxygen or non-invasive ventilation at enrollment with a median of 10 days to recovery compared with 18 days in control group (RRR 1.5, 95% CI 1.1 to 2.1) and the best clinical improvement by day 15 (OR 2.2; 95%

Appendix D - ACTT-4: Baricitinib/Remdesivir vs Dexamethasone/Remdesivir

CI 1.4 to 3.6). Baricitinib also showed benefit to those on low flow oxygen with a median of 5 days to recovery compared with 6 days in control group (RRR 1.17, 95% CI 0.98 to 1.39) and the clinical improvement by day 15 (OR 1.2; 95% CI 0.9 to 1.6). Patients who received combination treatment with baricitinib and remdesivir and those in the control arm had a similar incidence of adverse and serious adverse events including infections and venous thromboembolic events (VTE). On November 19, 2020, the FDA issued an Emergency Use Authorization (EUA) for the use of baricitinib in combination with remdesivir in hospitalized adults and children aged ≥ 2 years with COVID-19 who require supplemental oxygen, invasive mechanical ventilation, or extracorporeal membrane oxygenation (ECMO).

The Randomized Evaluation of Covid-19 Therapy (RECOVERY) trial is a controlled, open-label randomized trial, involving all major hospitals in the UK. The trial compared a range of possible treatments in patients who were hospitalized with Covid-19. Included, was a treatment arm assigned to receive oral or intravenous dexamethasone (at a dose of 6 mg once daily for up to 10 days) or to received usual care alone. Overall, 22.9% in the dexamethasone group and 25.7% in the usual care group died within 28 days after randomization (age-adjusted rate ratio, 0.83; 95% confidence interval [CI], 0.75 to 0.93; $P < 0.001$). In the dexamethasone group, the incidence of death was lower than that in the usual care group among patients receiving invasive mechanical ventilation (29.3% vs. 41.4%; rate ratio, 0.64; 95% CI, 0.51 to 0.81) and among those receiving supplemental oxygen without invasive mechanical ventilation (23.3% vs. 26.2%; rate ratio, 0.82; 95% CI, 0.72 to 0.94) but not among those who were receiving no supplemental oxygen respiratory support at randomization (17.8% vs. 14.0%; rate ratio, 1.19; 95% CI, 0.91 to 1.55). Remdesivir was not used routinely in the RECOVERY trial.

The ACTT-2 and RECOVERY trials are very different:

- ACTT 2 randomized patients to baricitinib, a JAK inhibitor and RDV or RDV alone. RECOVERY randomized patients to dexamethasone or standard care.
- Different study populations – ACTT-2 had more restrictive study criteria due to the use of remdesivir and baricitinib. Exclusions for liver or renal dysfunctions or cytopenias may have selected for a less ill population compared to RECOVERY.
- Different baseline mortalities – the ACTT-2 study had a mortality of 5.1-7.8% compared to 22.9-25.7% in RECOVERY. Even when directly comparing the study population that were not on supplemental oxygen at study entry - the ACTT-2 study had no deaths compared to 14.0-17.8% in RECOVERY.
- Study periods - The trials were conducted at slightly different periods early in the pandemic. RECOVERY was conducted March 19 to June 8 and ACTT-2 was conducted May 8-June 30.
- Antivirals - All subjects in ACTT-2 were given remdesivir whereas only 3 (< 1%) in RECOVERY were given remdesivir.
- Blinded - ACTT-2 was a double-blind randomized control trial and RECOVERY was open label (i.e., not blinded).

Given the above, direct comparison of these studies is difficult. However, the relative risk ratios also suggest these two anti-inflammatory strategies may be optimal in different inpatient

Appendix D - ACTT-4: Baricitinib/Remdesivir vs Dexamethasone/Remdesivir

populations, with baricitinib having the larger effect in the high flow or low flow oxygen group and dexamethasone having the largest effect in those on mechanical ventilation (see [Table 2](#)).

Table 2. Mortality from ACTT-2 and RECOVERY trials.

| | Overall | | Ordinal Score at Baseline | | | | | | | |
|-----------------------------------|------------------------------|-----------------------------|---------------------------|----------------------------|--------------------------|-----------------------------|---------------------------------|-----------------------------|-------------------------------------|----------------------------|
| | | | 4 Not on oxygen | | 5 Low flow oxygen | | 6 High flow oxygen / NIMV | | 7 Mechanical ventilation/ECMO | |
| Mortality- ACTT-2 | | | | | | | | | | |
| | Bari + RDV (n=515) | Placebo + RDV (n=518) | Bari + RDV (n=70) | Placebo + RDV (n=72) | Bari + RDV (n=287) | Placebo + RDV (n=276) | Bari + RDV (n=104) | Placebo + RDV (n=113) | Bari + RDV (n=54) | Placebo + RDV (n=57) |
| Hazard ratio (95% CI) | 0.65 (0.39, 1.08); p=0.09 | | NE | | 0.4 (0.14, 1.14) | | 0.55 (0.22, 1.37) | | 1.00 (0.45, 2.22) | |
| 28 Day mortality % (95% CI) | 5.1 (3.5, 7.6) | 7.8 (5.7, 10.6) | 0 (NE, NE) | 0 (NE, NE) | 1.9 (0.8, 4.4) | 4.7 (2.7, 8.1) | 7.4 (3.6, 15.0) | 12.9 (7.7, 21.3) | 23.1 (13.8, 37.1) | 22.6 (13.5, 36.4) |
| Mortality – RECOVERY Trial | | | | | | | | | | |
| | Overall | | No oxygen | | Oxygen only | | | Mechanical ventilation | | |
| | Dex (n=2104) | Usual Care (n=4321) | Dex (n=501) | Usual Care (n=1034) | Dex (n=1279) | Usual Care (n=2604) | Dex (n=324) | Usual Care (n=683) | | |
| Hazard ratio for mortality | 0.83 p<0.001 | | 1.19 | | 0.82 | | | 0.64 | | |
| 28 Day mortality % | 22.9 | 25.7 | 17.8 | 14.0 | 23.3 | 26.2 | 29.3 | 41.4 | | |

For this reason, direct comparison of these two anti-inflammatory interventions is important. ACTT-4 will evaluate patients hospitalized with COVID-19 and requiring oxygen and determine if baricitinib or dexamethasone (both in addition to remdesivir) is superior or if they are comparable.

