APPENDIX D - ACTT-4: BARICITINIB/REMDESIVIR Vs. DEXAMETHASONE/REMDESIVIR

1. PROTOCOL SUMMARY

1.1 ACTT-4 – Synopsis

Study overview

Severe COVID-19 is marked by a hyperinflammatory state characterized by upregulation of multiple cytokines. Multiple therapeutic strategies have been proposed to counter this inflammatory phase. To date, only two anti-inflammatory medications have demonstrated efficacy in large randomized trials – dexamethasone and baricitinib.

In the Randomized Evaluation of Covid-19 Therapy (RECOVERY) trial, treatment with dexamethasone demonstrated a lower mortality rate, 22.9% in the dexamethasone group versus 25.7% in the usual care group (absolute difference 2.8%; $p<0.001$).⁽¹⁵⁾ In ACTT-2, treatment with baricitinib in addition to remdesivir demonstrated a shorter median time-to-recovery of 7 days versus 8 days with remdesivir alone [rate ratio for recovery 1.16, $P=0.03$] and a lower 28-day mortality of 5.1% and 7.8% in the combination and control arms, respectively (absolute difference 2.7%; $P>0.05$). (Kalil et al, 2020)

These two studies, however, are very different – different study populations, different baseline mortality rates, and different data collected. Only ACTT-2 was blinded, and only in ACTT-2 was the anti-inflammatory intervention given in addition to an antiviral. Therefore direct comparison of these studies to determine which interventions are of value in which populations is difficult. ACTT-4 will evaluate adult patients hospitalized with COVID-19 and requiring supplemental oxygen by low flow, high flow or non-invasive mechanical ventilation modalities to determine if baricitinib or dexamethasone in combination with remdesivir are more effective at preventing progression to mechanical ventilation or death (among other outcomes) or if they are similar.

Enrollment Period:

It is anticipated the enrollment will be completed in 3-4 months.

General

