9. STATISTICAL CONSIDERATIONS

9.1 Statistical Hypotheses

The null hypothesis of no difference in the proportion of patients surviving without requiring invasive mechanical ventilation between baricitinib/remdesivir and dexamethasone/remdesivir will be tested using a superiority test.

A key secondary hypothesis will test whether the distribution of the 8-point ordinal scale at Day 15 differs between baricitinib/remdesivir and dexamethasone/remdesivir. For this key secondary hypothesis, the parameter of interest is the “common odds ratio,” which quantifies the shift in the severity distribution resulting from treatment. The null hypothesis to be tested is that the odds of improvement on the ordinal scale is the same for the control and experimental treatment arms (i.e., the common odds ratio is 1). An odds ratio greater than 1 quantifies an improvement in disease severity for the experimental treatment relative to its control. It is worth noting that, for large sample sizes, the test based on the proportional odds model is nearly the same as the Wilcoxon rank sum test.

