Appendix D - ACTT-4: Baricitinib/Remdesivir vs Dexamethasone/Remdesivir

differences between the ACTT-2 and RECOVERY studies as discussed above. In [Table 9](#), the first row of treatment effects is based on estimates from the ACTT-2 and RECOVERY results amongst the cohort that most closely resembles the ACTT-4 target population (those in ordinal 5 and 6). In the second row, the relative findings were changed to assume a gradual improvement in standard of care. This corresponds to a sample size of 1382 subjects. Sample size calculations were based on an exact unconditional score test of proportions using StatXact v11.1.0. Assuming 8% lost to follow-up, the sample size is planned to be approximately 1500 subjects.

The remaining lines demonstrate the power of the proposed sample size. There is good power of this trial for multiple scenarios unless the proportions surviving without invasive mechanical ventilation is much higher than anticipated (thought to be unlikely) or the difference in the proportions is smaller than anticipated (possible, but difficult to anticipate given the data available).

The formal analyses will be based on Kaplan-Meier estimates of the proportion of patients surviving without mechanical ventilation by Day 29 using a large sample normal approximation with Greenwood's variance formula. Accordingly, power for the final analysis is assumed to be equal or slightly higher than the power for the exact score as seen below.

Table 9: Sample size estimates and study power.

| | Total Sample Size | Proportion Dex Arm Surviving Through Day 29 Without Mechanical Ventilation | Proportion Bari Arm Surviving Through Day 29 Without Mechanical Ventilation | Power (unconditional exact score) | Power (KM + Greenwood) |
|--|-------------------|--|---|-----------------------------------|------------------------|
| - Baricitinib from ACTT-2 (OS 5 and 6) - Dexamethasone relative efficacy (only those on oxygen) from RECOVERY applied to ACTT-2 placebo arm | 1342 | 0.814 | 0.87 | 80.9% | 80.6% |
| Estimate of the above proportion applied to current outcomes given gradual improvement in care | 1382 | 0.85 | 0.9 | 80% | 80.5% |
| | | | | | |
| Other scenarios showing study power for the sample size of 1382 | 1382 | 0.9 | 0.95 | 94.5% | 94.9% |
| | 1382 | 0.9 | 0.925 | 37.0% | 37.5% |
| | 1382 | 0.85 | 0.925 | 99.4% | 99.4% |
| | 1382 | 0.8 | 0.875 | 96.6% | 96.6% |
| | 1382 | 0.8 | 0.85 | 68.2% | 68.9% |

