9.4 Statistical Analyses

9.4.1 General Approach

This is a double-blind, placebo controlled randomized trial testing a superiority hypothesis with a two-sided type I error rate of 5%. Secondary hypotheses have been ordered according to relative importance, with one key secondary hypothesis highlighted. These will be described according to the appropriate summary statistics (e.g., proportions for categorical data, means, medians for time-to-event data) and 95% confidence intervals.

A statistical analysis plan will be developed and filed with the study sponsor prior to unblinding of study and database lock.

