9.4.2 Analysis of the Primary Efficacy Endpoint

The primary efficacy analysis is a test of superiority of the proportion invasive mechanical ventilation free survival between the two treatment arms at Day 29. The test statistic will be a large sample test of the difference in Kaplan-Meier based estimates of the 28-day probability of mechanical ventilation free survival with a two-sided type I error rate of 0.05. The test of difference will assume asymptotic normality and use Greenwood's variance formula. (44)

If null hypothesis for the overall population is rejected, the analysis will proceed to test the null hypothesis within each baseline ordinal scale subgroup following the strategy described below.

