9.4.9 Multiplicity Adjustment

A fixed sequence testing scheme will control the overall family-wise Type I error rate at a two-sided α level of 0.05. If the primary hypothesis is rejected at two-sided $\alpha < 0.05$, hypothesis testing will proceed to four key secondary endpoints. Hypothesis testing will follow the fixed ordering below (see figure):

- 1) Proportion not progressing to ordinal scale 7 or 8;
- 2) Day 15 clinical improvement on ordinal scale;
- 3) Proportion not progressing to ordinal scale 6, 7 or 8 (amongst baseline ordinal scale 5 only);
- 4) Overall mortality (Day 29); and
- 5) Time to recovery (Day 29).

Hypothesis testing will continue at the next endpoint with $\alpha = 0.05$ only if the previous hypothesis is rejected at $\alpha=0.05$. This method of carrying forward the α -level from the previous test is described in the FDA guidance on Multiple Endpoints in Clinical Trials [<https://www.fda.gov/regulatory-information/search-fda-guidance-documents/multiple-endpoints-clinical-trials-guidance-industry>].

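### ACTT-4 promises to show whether the two drugs are superior or comparable, but its design is superiority only, so a non-significant result cannot support comparable

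*Protocol*

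**What the plan says.** Two places in Appendix D give the trial a purpose with two possible answers.

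- The study overview in 1.1 says the trial will establish whether the drugs, given with remdesivir, "are more effective at preventing progression to mechanical ventilation or death (among other outcomes) or if they are similar".
- The last paragraph of 2.1.1 says it will "determine if baricitinib or dexamethasone (both in addition to remdesivir) is superior or if they are comparable".

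The statistical sections provide for only one of these answers.

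- 9.1: the null hypothesis of no difference "will be tested using a superiority test".
- 9.2: Table 9 sizes the trial at 1382 evaluable subjects to detect 0.85 versus 0.90, and every row gives power to detect a difference.
- 9.4.1: the trial is described as "testing a superiority hypothesis with a two-sided type I error rate of 5" percent.
- 9.4.2: "The primary efficacy analysis is a test of superiority of the proportion invasive mechanical ventilation free survival between the two treatment arms at Day 29".
- 9.4.9: each step of the fixed sequence is a rejection of a no-difference null.

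Appendix D gives no equivalence or non-inferiority hypothesis, no margin, no interval criterion and no power for similarity. The objectives table in section 3 is neutral: it evaluates one arm versus the other.

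**The concern.** Failing to reject a null of no difference does not show that two treatments are similar. That conclusion needs a stated margin, or at least a rule for how narrow the interval must be. As the protocol stands, the only available route to *similar* or *comparable* is non-significance.

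This matters because both arms are active and 2.2.3.2 and 2.2.4.2 present the trial as a way to learn which anti-inflammatory strategy is best in which population. Section 9.2 itself concedes that the true difference may be smaller than anticipated. A null result would then fit the announced second answer, although the data might still be compatible with a difference of several points.

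**Working it through.** **Inputs.** From 9.2 and Table 9: 0.85 (dexamethasone) versus 0.90 (baricitinib), two-sided alpha 0.05, 1382 evaluable subjects, 8% loss, about 1500 enrolled. From 6.1: 1:1 allocation, so 691 per arm.

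**Step 1. Reproduce the plan's figure.** With unpooled variance, n per arm = (1.96 + 0.842)² × (0.85×0.15 + 0.90×0.10) / 0.05² = 7.85 × 0.2175 / 0.0025, which gives 683, or 1366 in total. The pooled formula gives 686, or 1372. The plan's 1382 comes from an exact test, so the agreement is good. Power at 691 per arm: SE = √(0.2175/691) = 0.01774, and Φ(0.05/0.01774 − 1.96) = 80.5%, which matches the Kaplan-Meier column. The sample size is sound for superiority.

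**Step 2. Non-significance at half the design difference.** Table 9 gives 37.0% (exact) and 37.5% (Kaplan-Meier) power for 0.90 versus 0.925. Check: SE = √((0.09 + 0.069375)/691) = 0.01519, and Φ(0.025/0.01519 − 1.96) = 37.7%. A real 2.5-point difference is therefore non-significant about 63% of the time.

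With dexamethasone at 0.85, the same formula gives:

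| True difference (points) | Probability of non-significance |
|---|---|
| 2.5 | 73% |
| 3 | 63% |
| 4 | 40% |
| 5 | 19.5% |

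**Step 3. Width of the interval.** Half-width = 1.96 × √(2p(1−p)/691).

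- p = 0.85: 1.96 × 0.01921 = 3.8 points.
- p = 0.90: 1.96 × 0.01614 = 3.2 points.

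A just-non-significant estimate lies about one half-width from zero, so its far limit is about two half-widths away: 2 × 3.16 = 6.3 points to 2 × 3.77 = 7.5 points. Both exceed the 5-point design effect. If all 1500 subjects contributed fully (750 per arm), the half-widths would be 1.96 × √(0.255/750) = 3.6 and 1.96 × √(0.18/750) = 3.0 points. The far limits would be about 7.2 and 6.1, still beyond 5.

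**Step 4. What a formal similarity claim would need.** The protocol gives no margin, so these figures rest on assumed margins. With truly equal arms, the chance that the whole interval lies within ±m is 2Φ(m/SE − z) − 1, floored at zero. Here z = 1.96 for a 95% interval and 1.645 for a 90% interval, with 691 per arm and rates from 0.85 to 0.90.

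| Assumed margin (points) | 95% interval rule | 90% interval rule |
|---|---|---|
| ±3 | about 0% | 0 to 17% |
| ±4 | 10 to 40% | 34 to 60% |
| ±5 | 48 to 75% | 66 to 85% |

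**The case against.** The strongest reply is that the two phrases are rationale prose. The objectives table is neutral, and the hypothesis, general approach, primary analysis and testing sequence agree with one another. The synopsis also refers to other outcomes, so *similar* there may be loose description. This stands, and it lowers the weight of the point. It does not remove the mismatch, because the reader is told twice that the trial can return an answer for which it has no criterion.

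A second reply is that interval reporting is partly present and that interpretation belongs in the SAP. Section 9.4.3 gives differences in proportions with 95% intervals for binary data, and 9.4.1 mentions 95% intervals, although its sentence refers to the secondary hypotheses. Section 9.4.2 states no interval for the primary difference. Reporting detail can indeed wait for the SAP, which is not shown. A similarity criterion is different, because it is tied to the hypothesis and sample size that the protocol has already fixed as superiority.

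Three stronger readings are tempting, and the protocol does not support them.

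- A reader might infer from Table 9 that non-significance is the usual result even when the arms differ materially. Six of its seven rows have exact power above 50% (80.9, 80, 94.5, 99.4, 96.6 and 68.2%). Only the 37.0% row does not, and 9.2 openly says power suffers if the difference is smaller than anticipated.
- A reader might infer that the sponsor plans to declare the drugs comparable on a non-significant test. No section says so.
- A reader might conclude that a 5-point margin should simply be added. That margin equals the difference the trial is sized to detect, so it would allow *comparable* to cover differences well above the 2.5 points at issue in step 2. Its power also depends on the choice of 95% or 90% intervals.

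**Conclusion.** The point holds as a mismatch between stated purpose and design. Appendix D 1.1 and 2.1.1 promise an answer of *similar* or *comparable* that a superiority-only plan cannot give. At the planned size, a non-significant primary result could leave a difference of about 6 to 7.5 points inside the 95% interval, against a design effect of 5 points. In the protocol's own 0.90 versus 0.925 scenario, the real difference is missed about 63% of the time.

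These figures assume 691 evaluable subjects per arm, rates between 0.85 and 0.90, and a normal approximation that reproduces Table 9. The mismatch itself does not depend on any assumed margin. The superiority test and the sample size behind it are not in question. The change is worth making because it limits what may be concluded, but it is a matter of wording.

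**What to change.** 1. In Appendix D 1.1 and 2.1.1, replace the clause offering *similar* or *comparable* as an outcome with a statement that the trial tests whether the two regimens differ.
2. In 9.4.2, add that a non-significant primary result will be reported as the difference in 28-day Kaplan-Meier estimates with its 95% confidence interval, and will not be taken as evidence of similarity.

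This changes text only; sample size, data collection and conduct are unaffected. The cost is a less favourable statement of what the trial can conclude. If any equivalence power is quoted, it should be labelled as resting on an assumed margin and shown under both the 95% and the 90% interval rule.
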